8.4 Missing Data

For primary analysis, no imputation will be used.

For the sensitivity analysis of LDL-C missing postbaseline LDL-C data for Week 6 will be imputed by last observation carried forward (LOCF) method based on the last valid postbaseline measurement prior to the visit.

Baseline values will not be used for imputation purpose..

Missing safety data will not be imputed.

Unless otherwise specified in the relevant section, partial date handling is described in Appendix 1.

8.5 Examination of Subgroups

Subgroup analyses will be conducted as stated in the exploratory analysis section 15.3.

The following subgroups will be assessed and described within the exploratory analysis sections:

- Sex: Female, Male
- Age (years): <65, ≥65
- History of statin administration: Yes, No (refer to section 8.3 for categorization)
- Status of a dose up-titration at Week 6: Yes, No
 - Yes (if study treatment dose is increased at Visit 3)
 - No (if study treatment dose is unchanged at Visit 3)

8.6 Randomization Schedule

In Visit 2, randomization is performed on patients who meet the inclusion criteria and do not meet any of the exclusion criteria and will be distributed 1:1 between test group (arm Eze/Ato) and control group (arm Ato).

Document: Document path and title

Template No.: CCI

Reference: CCI

Effective Date: 15Oct2021

All patients will be centrally assigned to randomized study intervention using an interactive web response system (IWRS).

Stratified block randomization

The randomization code will be set so that the test group and control group can be assigned in a 1:1 ratio by the stratified block randomization method for each institution and using statin administration history as a stratification factor.

9. OUTPUT PRESENTATIONS

Appendix 2 shows conventions for presentation of data in outputs.

10. DISPOSITION AND WITHDRAWALS

Participant disposition table will be based on the patients who were randomized.

The following summaries will be included in the disposition table: the number of patients who were randomized and the numbers and percentages of patients who were treated (= received at least one study medication), not treated, completed the study, and discontinued from the study overall with the reason of discontinuation by treatment group and total. Possible reasons for discontinuation include: violation of inclusion/exclusion criteria, lost to follow-up, aspartate aminotransferase (AST) or alanine aminotransferase (ALT) level $> 3 \times$ upper limit of normal (ULN) for 2 consecutive times, creatine kinase (CK) $> 10 \times$ ULN for 2 consecutive times, pregnancy, termination of the study by the investigator or Sponsor, difficult to continue the study according to the judgment of the investigator, adverse event, informed consent withdrawal and other.

A listing of patients who were discontinued from the study early will be provided. The listing will identify the visits completed and when the study was discontinued including the corresponding reasons, participant number, institution name, treatment group, sex, age, date of informed consent, and date of last visit as necessary.

Document: Document path and title

Template No.: CCI

Reference: CCI

Effective Date: 15Oct2021

The number and percentage of patients who failed screening (i.e. were not randomized) will be presented by reason among all enrolled patients. Possible reasons for screen failures include: violation of inclusion/exclusion criteria, informed consent withdrawal and other. A listing of all screen failures along with the corresponding reason will also be presented including participant number, institution name, sex, age, and date of informed consent.

The number and percentage of patients who were excluded from each of the SAS, FAS, and PPS will be presented by treatment group and total. Possible reasons for exclusion from each of analysis sets are found in section 6.

A listing of patients along with the analysis set that they were excluded from and the corresponding reasons will also be presented including participant number, institution name, treatment group, sex, age, date of informed consent, and status of study completion/discontinuation.

The number and percentage of patients with major protocol deviations will be presented overall and by deviation category and by treatment group and total.

A listing of patients with major protocol deviations will also be presented including the corresponding deviation category, participant number, institution name, treatment group, sex, age, date of informed consent, and status of study completion/discontinuation.

11. BASELINE CHARACTERISTICS

11.1 Demographic and Other Baseline Characteristics

Demographic data and other baseline characteristics will be presented for the FAS.

No statistical testing will be carried out for demographic or other baseline characteristics.

The following demographic and other baseline characteristics will be reported for this study:

- Age (years)
- Age categories: <65, ≥65
- Sex: Male, Female
- Height (cm)
- Weight (kg)
- Body mass index (BMI) (kg/m²)
 - BMI (kg/m²) = weight (kg)/ height (m)²

Document: Document path and title

Template No.: CCI

Reference: CCI

Effective Date: 15Oct2021

- Smoking history: Currently smoking, Past smoker, Never smoked
- Alcohol history: Now drinking, Past drinking, Never
- Alcohol consumption (only in case of 'Now drinking'): Less than 2 drinks a week, 2 to 3 drinks a week, 4 or more drinks a week

Continuous variables will be summarized using number of patients without missing values, mean, standard deviation, median, 1st quartile, 3rd quartile, minimum, and maximum by treatment group and total. Categorical variables will be summarized using the total number of patients without missing values and the number and percentage of patients for each category by treatment group and total.

11.2 Medical and Treatment History Related to Dyslipidemia

Medical and treatment history related to dyslipidemia will be presented for the FAS.

The following information on medical and treatment history related to dyslipidemia will be reported:

- Dyslipidemia duration (years): (randomization date – dyslipidemia diagnosis date + 1) / 365.25
 - Unknown date and/or month of the dyslipidemia diagnosis date will be replaced by 1
 - Missing or unknown year of the dyslipidemia diagnosis date will not be replaced and dyslipidemia duration will be considered missing
- Medical history related to dyslipidemia including acute coronary syndrome (ACS) (myocardial infarction (MI) or unstable angina (UA)), stable angina, coronary revascularization (percutaneous coronary intervention (PCI)), coronary artery bypass graft surgery (CABG) and other arterial revascularization procedures), stroke, transient ischemic attack, peripheral arterial disease, and other clinical or unequivocal ASCVD on imaging: Yes (prior or current), No
- Family history status: Yes, No
 - Yes: if any of 'father', 'mother', 'brothers/sisters', 'Others' is selected
 - No: if none is selected
- Family history: father, mother, brothers/sisters, other
 - As a multiple choice item, categories are not mutually exclusive
- History of statin administration: Yes (\geq 4 weeks), No (<4 weeks, Naïve)
- Baseline LDL-C (mg/dL)
- Baseline LDL-C categories: <130, \geq 130 to <160, \geq 160
- Baseline HDL-C (mg/dL)

Document: Document path and title

Template No.: CCI

Reference: CCI

Effective Date: 15Oct2021

- Baseline non-HDL-C (mg/dL): defined as (total cholesterol – HDL-C)
- Baseline triglycerides (mg/dL)
- Baseline total cholesterol (mg/dL)

Continuous variables will be summarized using number of patients without missing values, mean, standard deviation, median, 1st quartile, 3rd quartile, minimum, and maximum by treatment group and total. Categorical variables will be summarized using the total number of patients without missing value and the number and percentage of patients for each category by treatment group and total.

12. GENERAL MEDICAL HISTORY

Medical History information will be presented for the FAS.

All data on medical history will be categorized as medical history or concomitant illness using the following definitions, which will be summarized respectively.

- Medical history: any condition with the ongoing status that is 'No'
- Concomitant Illness: any condition with the ongoing status that is 'Yes'

For each medical history and concomitant illness, the number and percentage of patients will be summarized overall and by MedDRA SOC and PT for treatment group and total.

13. MEDICATIONS

Medications will be presented for the FAS.

All data on medications will be categorized as prior or concomitant using the following definitions, which will be summarized respectively. See Appendix 1 for handling of partial dates.

- Prior medications: any medication with a stop date that is prior to the first administration of the study drug.
- Concomitant medications: any medication with a stop date that is on or after the first administration of the study drug or any medication with the ongoing status that is 'Yes'.

Document: Document path and title

Template No.: CCI

Reference: CCI

Effective Date: 15Oct2021

For each prior and concomitant medications, the number and percentage of patients will be summarized overall and by WHO-DD therapeutic subgroup and preferred name for treatment group and total.

14. MEDICAL PROCEDURES

Medical procedures will be presented for the FAS.

All data on procedures will be categorized as prior or concomitant using the following definitions, which will be summarized respectively. See Appendix 1 for handling of partial dates.

- Prior procedures: any procedure with a stop date that is prior to the first administration of the study drug.
- Concomitant procedures: any procedure with a stop date that is on or after the first administration of the study drug or any procedure with the ongoing status that is 'Yes'.

For each prior and concomitant procedures, the number and percentage of patients will be summarized overall and by MedDRA SOC and PT for treatment group and total.

15. EFFECTIVENESS OUTCOMES

15.1 Primary Effectiveness

15.1.1 Primary Effectiveness Variable & Derivation

The primary objective of this study is to evaluate the effectiveness of early add-on of ezetimibe with atorvastatin in very high-risk patients.

The primary endpoint is percentage change in LDL-C from baseline (Visit 1) to week 6 (Visit 3).

15.1.2 Primary Analysis of Primary Effectiveness Variable

The primary endpoint analysis will be performed on the FAS.

The statistical hypothesis of this study is as follows.

$$H_0: \mu_t - \mu_c = 0 \text{ vs. } H_1: \mu_t - \mu_c \neq 0$$

Document: Document path and title

Template No.: CCI

Reference: CCI

Effective Date: 15Oct2021

μ_t = Percentage change in LDL-C from baseline to 6 weeks in ezetimibe/atorvastatin 10/40 mg
 μ_c = Percentage change in LDL-C from baseline to 6 weeks in atorvastatin 40 mg

The primary endpoint will be analyzed by fitting an ANCOVA model with treatment group (Eze/Ato, Ato) and history of statin administration (Yes, No) as fixed effects and baseline LDL-C as a covariate. In addition to descriptive statistics for LDL-C at each visit and its percentage change from baseline by treatment group, least squares (LS) means for each treatment group with corresponding standard errors (SEs) and treatment differences of LS means with corresponding two-sided 95% confidence interval (CI) and p-value which will be derived from the fitted model will be presented. If the upper limit of the 95% two-sided CI for the corresponding treatment difference (Eze/Ato - Ato) is less than 0, Eze/Ato is considered superior to Ato.

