5.1 Inclusion Criteria

Participants are eligible to be included in the study only if all of the following criteria apply:

1. Patients who are ≥ 30 years old.
2. Patients with very high-risk*
*: clinical or unequivocal on imaging ASCVD. ASCVD includes previous ACS (MI or UA), stable angina, coronary revascularization (percutaneous coronary intervention (PCI), coronary artery bypass graft surgery (CABG), and other arterial revascularization procedures), stroke and transient ischaemic attack (TIA), and peripheral arterial disease (Mach F 2020).
3. Patients (a) who failed to achieve LDL-C lower than 70 mg/dL with low and/or moderate intensity^{\$} statin mono therapy for ≥ 4 weeks or (b) who are statin-naïve or have not been on a stable (unchanged) statin regimen for at least 4 weeks prior to enrollment.
\$: rosuvastatin < 20 mg, atorvastatin < 40 mg, and all dose of pitavastatin, simvastatin, lovastatin, pravastatin, and fluvastatin (Stone NJ 2014).
4. Patients with LDL-C levels ≥ 70 mg/dL
5. Patients who are willing to maintain TLC throughout the study.
6. Patients who are willing to provide written informed consent prior to study enrollment.

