6.7 Concomitant Therapy

The Investigator must instruct the participant to notify the study site about any new medications he/she takes after signing the study informed consent. All medications, procedures, and significant non-drug therapies (including physical therapy and blood transfusions) administered after the participant was enrolled into the study must be recorded on the appropriate eCRFs.

Any therapy that the participant is receiving at the time of enrollment or receives during the study must be recorded along with:

- Concomitant therapy name
- Reason for use
- Period including start and end dates

In particular, in the case of medication, the following items are also collected:

- Route of administration
- Dosage information including dose and frequency

Prior medication up to 1 month prior to enrollment is also collected.

The following drugs are not allowed to be administered during the clinical trial period. However, partial permission is possible at the discretion of the investigator.

1. Lipid modulating agents other than IMP.
 - statin, fibric acid derivatives, ezetimibe, bile acid sequestrants, PCSK9 inhibitor, nicotinic acid (niacin)
 - alipogene tiparvovec, bempedoic acid, dextrothyroxine, inclisiran, lomitapide, magnesium pyridoxal 5-phosphate glutamate, meglitol, mipomersen, omega-3 triglycerides incl. other esters and acids, policosanol, probucol, tiadenol
2. Other drugs or foods that may affect blood lipids.
 - systemic steroids, lipolytic enzyme inhibitors (e.g., orlistat), hormone replacement therapy, thyroid therapy (e.g., levothyroxine, benzylthiouracil), fish oil, fiber-based laxatives, cholestine, phytosterol margarines, grapefruit.
3. Drugs with known drug interactions with IMP according to label.
 - cyclosporine, HIV protease inhibitors, hepatitis C protease inhibitors, gemfibrozil, fusidic acid.
4. Drugs or foods described in the label precautions.

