9.5 Sample Size Determination

The statistical hypothesis of this study is as follows.

$$H_0: \mu_t - \mu_c = 0 \text{ vs. } H_1: \mu_t - \mu_c \neq 0$$

$$\mu_t = \text{Percentage change in LDL-C from baseline to 6 weeks in ezetimibe/atorvastatin 10/40 mg}$$

$$\mu_c = \text{Percentage change in LDL-C from baseline to 6 weeks in atorvastatin 40 mg}$$

Azar et al. reported that the between-treatment difference in percentage change in LDL-C at 8 weeks was -10% in favor of ezetimibe/atorvastatin 10/40 mg compared to atorvastatin 40 mg (-20% vs -10%; p-value=0.01) (Azar RR 2010). This is the only study that has assessed the efficacy of ezetimibe/atorvastatin 10/40 mg versus atorvastatin 40 mg among very high-risk patients with stable CAD or CAD equivalent (coronary stenosis >50%, previous myocardial infarction, percutaneous coronary intervention, coronary artery bypass graft surgery, diabetes

mellitus, stroke, peripheral vascular disease) who were taking the potency of the background statins ≤ 20 mg/day of atorvastatin prior to the randomization. Although the evaluation time point for the LDL-C lowering effect in Azar et al. study is at 8 weeks, it is noted that a reduction in LDL-C is usually achieved with all statins as well as ezetimibe as early as 2 weeks, with a maximum response occurring by 4 weeks and maintaining thereafter during continued therapy (ACH-Ezetimibe Product Monograph 2019; Shankar PR 2019). Given that, this study sets -10% as the expected difference in percentage change in LDL-C from baseline to 6 weeks between the treatment groups.

The pooled standard deviation of 19.0% was obtained from the p-value of 0.01 and a total of 50 patients per treatment group reported in the study of Azar et al.; The t-value that corresponds with a p-value of 0.01 and $50 + 50 - 2 = 98$ degrees of freedom is $t=2.627$, considering that the degrees of freedom are given $N_1 + N_2 - 2$, where N_1 and N_2 are the number of study patients per each treatment group. As the t-value is the ratio of the difference in means to the standard error of the difference in means, the standard error is therefore obtained by dividing 10 (treatment difference in percentage change in LDL-C) by 2.627, which gives 3.8066. In turn, the standard deviation obtained from standard error is 19% ($3.8066 / \text{SQRT}(1/50 + 1/50)$).

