Based on this, the number of patients in each treatment group calculated by the formula below is about 57 under the assumption of two-sided significance level $\alpha = 0.05$, power $1-\beta = 0.80$ with a randomization ratio $\lambda = 1$. Considering the dropout rate of 10%, 63 patients for each group and thus, a total of 126 patients will be randomized in this study.

$$n = \frac{(\gamma + 1)(Z_\alpha + Z_\beta)^2 \sigma^2}{\gamma(\mu_t - \mu_c)^2} = \frac{(1 + 1)(1.96 + 0.842)^2(19)^2}{(-10)^2} = 56.69$$

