4.2 Sample Size

The number of patients in each treatment group is about 57, assuming that the treatment difference in percentage change in LDL-C between Ezetimibe/Atorvastatin and Atorvastatin would be 10% with an SD of 19%. This calculation is based on a two-sided significance level $\alpha = 0.05$, power $1-\beta = 0.80$ with a randomization ratio $\lambda = 1$. Considering the dropout rate of 10%, 63 patients for each group and thus, a total of 126 patients will be randomized in this study.

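### The primary ANCOVA does not use the strength of the background statin, which can be derived from collected data: a modest, avoidable loss of precision, with no bias and no shortfall in planned power

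*SAP*

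**What the plan says.** SAP 15.1.2 fits treatment group and "history of statin administration (Yes, No) as fixed effects and baseline LDL-C as a covariate". Protocol 9.3.2 names the same covariates, and SAP 15.2.3 repeats the model for the continuous secondary endpoints other than triglycerides. SAP 8.3 derives the Yes/No term from one eCRF question on whether the patient has been on a statin for 4 weeks or more.

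Criterion 3(a) (Protocol 5.1) admits patients not at goal on low- or moderate-intensity monotherapy. A footnote defines this as "rosuvastatin < 20 mg, atorvastatin < 40 mg, and all dose of pitavastatin, simvastatin, lovastatin, pravastatin, and fluvastatin". From Visit 2 the control arm takes atorvastatin 40 mg and the test arm adds ezetimibe to it (Protocol 6.1).

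Protocol 6.7 states: "Prior medication up to 1 month prior to enrollment is also collected". For medications it also asks for dose and frequency, and Protocol 8.1.3 lists statin history among the dyslipidemia data. No efficacy model or subgroup (SAP 8.2, 8.5, 15) uses agent, dose or intensity. Agent appears only in the general medication summaries by preferred name (SAP 13).

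**The concern.** Stratum (b) is to stay below 40% of each group (Protocol 6.3.1), so most patients should be in stratum (a), where baseline LDL-C is an on-statin value. Moving to atorvastatin 40 mg is a larger step from a weak statin than from one just under the eligibility limit. Two patients with the same baseline LDL-C but different earlier statins may therefore have different expected percentage changes, and the model treats them alike. Randomisation is stratified by institution and statin history only, so strength within 'Yes' is balanced by chance alone. Any part of the response that strength explains stays in the residual and widens the primary confidence interval, although the information to remove it is collected.

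**Working it through.** **Inputs from the documents**
- Effect (Protocol 9.5): "this study sets -10% as the expected difference in percentage change in LDL-C from baseline to 6 weeks".
- SD 19 points (SAP 4.2; Protocol 9.5). Source: "The pooled standard deviation of 19.0% was obtained from the p-value of 0.01 and a total of 50 patients per treatment group".
- Two-sided alpha 0.05, power 0.80, 1:1 allocation.
- Stratum (a) above 60%, from the cap on (b).

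**Step 1: the plan's own figure.** t for p = 0.01 on 98 df is 2.627. SE = 10/2.627 = 3.807. SD = 3.807/√(1/50 + 1/50) = 19.03. Then n = 2 × (1.96 + 0.842)² × 19²/10² = 56.69, so 57 per arm. With 57 per arm the SE of the difference is 19 × √(2/57) = 3.559. Power = Φ(10/3.559 − 1.96) = 0.802, and the 95% CI half-width is 1.96 × 3.559 = 6.98 points. The plan's figure reproduces, and it takes no credit for any covariate.

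**Step 2: variance that an intensity term could explain.** Let s be the share in stratum (a), p the share of (a) on the weaker statin, and d the gap in expected percentage change between weaker and stronger background statins, taken as equal in both arms. The share of variance explained is

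R² = s × p(1 − p) × d²/361, where 361 = 19².

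The residual SD becomes 19 × √(1 − R²). The documents give no value for p, d or R². The assumed ranges are s 0.6-0.8, p 0.2-0.5 and d 5-15 points. The 19 is taken as the spread left after the SAP's covariates, and intensity is assumed not to overlap with baseline LDL-C.

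| s | p | d | R² | Power, 57 per arm | CI half-width | Equivalent patients per arm (57 × R²) |
|---|---|---|---|---|---|---|
| 0.6 | 0.20 | 5 | 2.4/361 = 0.007 | 0.805 | 6.95 | 0.4 |
| 0.6 | 0.35 | 10 | 13.65/361 = 0.038 | 0.817 | 6.84 | 2.2 |
| 0.8 | 0.35 | 10 | 18.2/361 = 0.050 | 0.822 | 6.80 | 2.9 |
| 0.8 | 0.50 | 15 | 45/361 = 0.125 | 0.852 | 6.53 | 7.1 |

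**Step 3: simulation.** The SAP model was run with and without the extra term, 57 per arm, 6,000 runs per case.
- s 0.8, p 0.3, d 10: power 0.787 without, 0.800 with; half-width 7.07 and 6.93.
- s 0.8, p 0.5, d 15: power 0.800 without, 0.847 with; half-width 7.08 and 6.64.
- Intensity explains nothing: half-width 7.07 without, 7.10 with.

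Simulated power without the term lies slightly below 0.802 mainly because the model uses the t distribution (0.795 by direct calculation). That has nothing to do with statin strength.

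**Step 4: what a large effect would need.** For power 0.90, R² must reach 0.25. With s 0.6-0.8 and p 0.3-0.5, that needs a gap of about 21-27 points. To explain half the variance, expected responses would have to vary across background statins with an SD of 19 × √0.5 = 13.4 points.

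**The case against.** The strongest reply is that the model already adjusts for baseline LDL-C and statin history, and that leaving out one more prognostic covariate is a legitimate choice. This stands in part: the omission is not an error and the plan is complete without the term. Four further points also stand.

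- **No low/moderate cut exists.** Criterion 3 gives one pooled list. The dividing line would have to be written into the SAP.
- **'Yes' is not stratum (a).** Stratum (b) includes patients whose regimen changed within 4 weeks. Such a patient, if on a statin for 4 weeks or more, is (b) at randomisation but 'Yes' under SAP 8.3. Criterion 3 sets no intensity limit for (b), so a two-level code could leave that patient unclassified.
- **The gain may be smaller than calculated.** On-statin baseline LDL-C may already carry part of the information, and nothing was deducted for that. Appendix 6 of the protocol also allows that the (b) ratio may differ from plan.
- **It departs from Protocol 9.3.2**, so it is more than a wording change.

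A reader might infer that the trial is underpowered because the term is missing. The documents do not support that. The 57 per arm uses the full SD of 19 with no covariate gain, and that SD comes from patients "who were taking the potency of the background statins" up to a stated limit, so it already contains some spread in potency. A reader might also infer that chance imbalance in statin strength biases the result. Under randomisation it does not, and the confidence interval allows for it.

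What the reply does not remove is that the data are collected and the term costs almost nothing even if it explains nothing.

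**Conclusion.** The point holds as a modest efficiency loss. Under the assumptions in the working, a background-intensity term explains about 1% to 12.5% of the planned variance, with 4-5% in the middle. Power goes from 0.80 to about 0.81-0.85 (about 0.82 mid-range), and the CI half-width from 6.98 to between about 6.5 and 6.95 points. The gap, the split and the absence of overlap with baseline LDL-C are all assumed; any overlap would reduce the gain.

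A reader might go further and infer that background potency largely determines how far LDL-C can fall. Nothing in the documents shows this, and the assumed ranges give at most one eighth of the variance. The supportable statement is that potency may influence the response.

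**What to change.** Amend SAP 8.3, 15.1.2 and 15.2.3 as follows, for the LDL-C, non-HDL-C and total cholesterol ANCOVAs:

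1. Use the randomisation stratum as recorded in the IWRS, in place of the duration item from the eCRF.
2. Add a pre-specified background-intensity term, for example none / low / moderate. State a category or pooling rule for patients on a statin who fall outside criterion 3(a).
3. Define the levels by an agent-and-dose table written into the SAP, for example from the guideline that criterion 3 cites. Assign them from pre-randomisation medication records only.
4. Because the trial is open-label, fix the table and the assignments before database lock and without access to outcomes.
5. Record the departure from Protocol 9.3.2 in SAP 4.5, which now states that nothing has changed.

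The cost is a coding step and one or two degrees of freedom: one if intensity is coded only within stratum (a), two for three levels beside the stratum. A separate level for patients outside criterion 3(a) would add one more, which a pooling rule avoids. If the database is already locked, leave the primary model unchanged and report this as a labelled supplementary analysis.
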